7.8 Follow-up Visit after 1 month on Truvada

This assessment will be required for women on immediate ART (1 month) and for women on deferred ART (post cessation of breastfeeding).

There will be an interview to see if the participant has experienced any side effects sufficient to interrupt Truvada, and how they are coping with the daily regimen. Urine will

be collected for analysis. A blood sample will also be collected for a HIV test, renal function test (creatinine), other routine antenatal investigations and specimen storage.

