No new adverse reactions to TRUVADA (TDF/FTC) were identified from two randomized placebo-controlled clinical trials (iPrEx, Partners PrEP) in which 2830 HIV-1 uninfected adults received TRUVADA once daily for pre-exposure prophylaxis [20,32]. Subjects were followed for a median of 71 weeks and 87 weeks, respectively. These trials enrolled HIV-negative individuals ranging in age from 18 to 67 years. The iPrEx trial enrolled only males or transgender females of Hispanic/Latino (72%), White (18%), Black (9%) and Asian (5%) race [31]. The Partners PrEP trial enrolled both males (61-64% across treatment groups) and females in Kenya and Uganda [20].

Laboratory Abnormalities: Six subjects in the TDF-containing arms of the Partners PrEP trial discontinued participation in the study due to an increase in blood creatinine compared with no discontinuations in the placebo group [20]. One subject in the TRUVADA arm of the iPrEx trial discontinued from the study due to an increase in blood creatinine and another due to low phosphorous [32].

In addition to the laboratory abnormalities described above, Grade 1 proteinuria (1+) occurred in 6% of subjects receiving TRUVADA in the iPrEx trial. Grades 2-3 proteinuria (2-4+) and glycosuria (3+) occurred in less than 1% of subjects treated with TRUVADA in the iPrEx trial and Partners PrEP trial.

Changes in Bone Mineral Density (BMD):

In clinical trials of HIV-1 uninfected individuals, decreases in BMD were observed. In the iPrEx trial, a substudy of 503 subjects found mean changes from baseline in BMD ranging from -0.4% to -1.0% across total hip, spine, femoral neck, and trochanter in the TRUVADA group compared with the placebo group, which returned toward baseline after discontinuation of treatment [33]. Thirteen percent of subjects receiving TRUVADA vs. 6% of subjects receiving placebo lost at least 5% of BMD at the spine during treatment. Bone fractures were reported in 1.7% of the TRUVADA group compared with 1.4% in the placebo group. No correlation between BMD and fractures was noted. The Partners PrEP trial found similar fracture rates between treatment and placebo groups (0.8% and 0.6%, respectively). No BMD evaluations were conducted during this trial [20].

1.11 Clinical Experience With and Safety of *Emtricitabine and Tenofovir Disoproxil* Fumarate (FTC and TDF) - Truvada in Pregnancy and Breastfeeding

Emtricitabine (FTC, Emtriva[™]) in animal studies

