To explore the safety of Truvada when used as PrEP in combination with current recommendations for prevention of sexually transmitted infections and HIV in young women at substantial risk of HIV acquisition during pregnancy and lactation.

2.2 Primary Objective:

 To compare the frequency and seriousness of specific adverse events related to TDF/FTC in women and their children in Arm A (exposure to TDF/FTC) and Arm B (no exposure to TDF/FTC) during pregnancy until breastfeeding cessation.

2.3 Secondary Objectives:

- To estimate HIV incidence in women in ARM A with ARM B at delivery and at 18 months post-delivery.
- To determine the interdependency of adherence to a once daily oral TDF/FTC regimen and standard HIV prevention methods during pregnancy and postdelivery.
- To measure antiretroviral drug (TDF/FTC) level in women and their infants in association with adherence, safety and level of protection (plasma and breastmilk)
- To detect drug resistance among women who acquire HIV infection and correlate the treatment outcomes (after initiating immediate ARV treatment) with drug resistance
- To determine mother-to-child transmission of HIV among women who acquire incident infections during pregnancy and breastfeeding and the frequency of drug resistance in their infected babies

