6.0 STUDY TREATMENT CONSIDERATIONS

The drug to be used in this study is Truvada (tenofovir disoproxil fumarate/ emtricitabine) which is the antiretroviral drug to be used to prevent HIV acquisition. TRUVADA tablets are fixed dose combination tablets containing emtricitabine and tenofovir disoproxil fumarate. EMTRIVA is the brand name for emtricitabine, a synthetic nucleoside analog of cytidine. Tenofovir disoproxil fumarate (tenofovir DF) is converted in vivo to tenofovir, an acyclic nucleoside phosphonate (nucleotide) analog of adenosine 5'-monophosphate. Both emtricitabine and tenofovir exhibit inhibitory activity against HIV-1 reverse transcriptase.

6.1 Study product formulation and storage conditions

Study Drug : Emtricitabine-Tenofovir disoproxil fumarate FTC-TDF Truvada[®] Formulation: 200 mg/300 mg tablets

Appearance: Blue, capsule shaped, film-coated tablet that are debossed with "GILEAD" on one side

Storage: 25°C (77°F) - Excursions permitted between 15-30°C (59-86°F). Keep container tightly closed. Each bottle contains thirty tablets with a silica gel desiccant canister that should remain in the original container to protect the product from humidity.

6.2 Treatment Procedures

- ARM A: Pregnant women allocated to ARM A will initiate Truvada on the day of randomization and will continue throughout peripartum until cessation of breastfeeding and thereafter given an option to continue PrEP until 18 months postdelivery.
- ARM B: Pregnant women allocated to ARM B will only initiate Truvada at cessation of breastfeeding and thereafter given an option to initiate PrEP until 18 months postdelivery.

6.3 Treatment Schedule

The treatment schedule is a once daily uninterrupted course.

6.4 Study product procurement

The study site pharmacist will order Truvada from the manufacturer (Gilead Sciences).

6.5 Study product accountability

The study pharmacist will maintain complete accountability and storage condition records of all study products received from Gilead Sciences and subsequently dispensed to study participants. All study products will be stored at the site study pharmacy. All unused study products will be returned to Gilead Sciences after the study is completed and terminated.

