8.5 Definitions

Adverse Event:

An adverse event (AE) is defined as any untoward medical occurrence in a clinical research participant administered an investigational product and which may or may not have a causal relationship with the investigational product. As such, an AE can be an unfavorable or unintended sign (including an abnormal laboratory finding, for example), symptom or disease temporally associated with the use of an investigational product, whether or not considered related to the product. Study participants will be instructed to contact the study clinician to report any AEs their infants may experience.

Serious Adverse Event:

A serious adverse event (SAE) is any untoward medical occurrence that at any dose that results in death, is life threatening, requires inpatient hospitalization or prolongation of existing hospitalization, results in persistent or significant disability/incapacity, or is a

congenital anomaly/birth defect (April 1996 International Conference on Harmonisation (ICH), Good Clinical Practice: Consolidated Guidance, (ICH E6). Important medical events that may not be immediately life – threatening or result in death or hospitalization but may jeopardize the patient or may require intervention to prevent one of the outcomes listed in the definition above may also be considered to be serious. (October 1994 ICH guidance (E2A), Clinical Safety Data Management: Definitions and Standards for Expedited Reporting).

SUSAR: Suspected, Unexpected Serious Adverse Reaction:

Serious (see SAE definition above)

Related (i.e. there is a reasonable possibility that the AE may be related to the study agent)

Unexpected (see definition below)

Unexpected AE:

An AE, the nature or severity (intensity) of which is not consistent with the applicable agent information (Investigator's Brochure, package insert, or summary of agent characteristics).

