The primary objective is to compare the frequency and seriousness of adverse events in women receiving tenofovir/emtricitabine in pregnancy and their newborn as opposed to women not receiving tenofovir/emtricitabine during pregnancy and their newborn. The number of adverse events experienced during pregnancy and post-delivery will be summarized for each of the study arms. This will also be stratified by seriousness of the adverse event. The number of adverse events will be compared between the study arms using Fisher's Exact test. Furthermore we will use the most widely used approach to test equivalence, namely the two one-sided test (TOST) procedure (Schuirmann DJ. A comparison of the two one-sided tests procedure and the power approach for assessing equivalence of average bioavailability. J Pharmacokin Biopharm. 1987;15:657–680. doi: 10.1007/BF01068419). Furthermore we will also employ a hierarchical or random effects modeling approach for a non-inferiority analysis for the primary endpoints.

A secondary objective is to compare the number of incident HIV infections in women during pregnancy alone and thereafter during breastfeeding. The analysis will be stratified by levels of PrEP adherence, partner involvement, condom usage and relationship dynamics. The cumulative incidence and associated 95% confidence intervals will be calculated for each study arm. The number of incident events will be compared for statistical difference between the study arms using Fisher's Exact test.

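### Study urine for mothers is scheduled only at the drug-triggered visit in section 7.8, so within the primary window any abnormality found on it adds to Arm A's adverse-event count alone

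*Combined protocol and SAP*

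**What the plan says.** Section 7.8 describes an assessment one month into Truvada: "This assessment will be required for women on immediate ART (1 month) and for women on deferred ART (post cessation of breastfeeding". It is mainly an interview about side effects and coping with the regimen. It adds that urine will "be collected for analysis. A blood sample will also be collected for a HIV test, renal function test (creatinine", among other blood tests. It does not say what the urine is analysed for.

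The two arms reach this visit at very different times. Under section 6.2, "Pregnant women allocated to ARM A will initiate Truvada on the day of randomization", whereas "Pregnant women allocated to ARM B will only initiate Truvada at cessation of breastfeeding". Section 7.11 makes clear that Arm B receives drug only if the woman chooses it. The primary objective (2.2) contrasts Arm A with "Arm B (no exposure to TDF/FTC) during pregnancy until breastfeeding cessation".

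Section 8.5 states that "an AE can be an unfavorable or unintended sign (including an abnormal laboratory finding, for example". Section 10.4 states: "The number of adverse events will be compared between the study arms using Fisher's Exact test". Appendix 5, which section 7.9 makes the schedule for every visit after enrolment, has no urine row.

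**The concern.** A randomised comparison of adverse-event counts is fair only if both arms have the same chance of having an event detected. Blood tests meet that condition here: 7.21 and Appendix 5 schedule them for all women at the same visits. Urine does not, because its only scheduled collection follows the drug and not randomisation. A urine abnormality that is equally common in both arms would be looked for by the study in Arm A during pregnancy and not looked for in Arm B until after the primary window. The resulting excess in Arm A would look like a drug effect. The finding is relevant to this drug, since section 1.10 reports proteinuria and glycosuria among Truvada recipients. No pre-drug urine is scheduled in either arm, so a woman's own baseline cannot be used to sort this out later.

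**Working it through.** **Step 1. Where maternal urine is scheduled.**

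| Place | Maternal urine? |
|---|---|
| 5.1, 7.4, 7.5 (screening, enrolment) | none listed |
| 7.8 (one month on Truvada) | yes, test not named |
| 7.12 (visits during product use) | none; blood and swabs |
| 7.21 (maternal safety assessments) | none; blood tests and DXA |
| Appendix 5 | no urine row |

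**Step 2. Scheduled study urine tests per woman inside the primary window (pregnancy until breastfeeding cessation).**

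- Arm A: drug starts at randomisation in pregnancy, so the one-month visit normally falls inside the window. Count = 1.
- Arm B: drug can start only when the window has closed, and only in women who choose it. Count = 0.

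**Step 3. Whether a finding reaches the between-arm count.** Section 8.5 admits abnormal laboratory findings as adverse events. Section 10.4 compares adverse-event numbers and has no rule restricting them to tests done in both arms. A 7.8 urine abnormality recorded as an event therefore enters on the Arm A side only.

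**Step 4. Urine-only illustration.** Inputs: n = 421 per arm (10.3). As a check on that figure, a non-inferiority calculation with 18.5% in both arms, margin 7.5 points, one-sided 0.025 and 80% power gives 421. Assumptions: the true rate r is the same in both arms, and abnormalities are detected only by scheduled study urine. Expected Arm A count = 421 × r, rounded; Arm B count = 0; two-sided Fisher's exact test.

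| r | 421 × r | Count A v B | p |
|---|---|---|---|
| 0.5% | 2.1 | 2 v 0 | 0.50 |
| 1% | 4.2 | 4 v 0 | 0.12 |
| 2% | 8.4 | 8 v 0 | 0.008 |
| 3% | 12.6 | 13 v 0 | 0.0002 |

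With the same test at the same time in both arms, the expected counts are equal and p = 1.0 in every row.

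**Step 5. Effect on the all-adverse-event comparison.** Section 10.4 names no urine-only test, so Step 4 overstates what the planned analysis would show. Suppose a share b of women in each arm has some other event, independently of urine findings, and women with any event are counted. Expected counts are 421 × [b + r(1 − b)] in Arm A and 421 × b in Arm B. At r = 2%:

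| b | Count A v B | p |
|---|---|---|
| 5% | 29 v 21 | 0.31 |
| 10% | 50 v 42 | 0.44 |
| 20% | 91 v 84 | 0.61 |
| 50% | 215 v 210 | 0.78 |

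At r = 1% and b = 5% the counts are 25 v 21 (p = 0.65). The shift always goes against Arm A, but other events dilute it. The values of b are assumptions; the documents give none.

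**The case against.** Several points on the other side stand.

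- **The analyte is not stated.** Section 7.8 does not say that urine is tested for protein or glucose, graded, or recorded as an event. The bias arises only if a result is recorded.
- **The plan's stated laboratory threshold is higher.** Section 10.3 describes maternal laboratory events as chemistry abnormalities of Grade 2 or above. Section 1.10 puts Grade 2–3 proteinuria and glycosuria below 1% on Truvada. At 1%, even the urine-only illustration gives p = 0.12.
- **No named main outcome is touched.** Creatinine clearance, pregnancy outcomes, bone density and growth (10.2) do not depend on maternal urine, and serum creatinine is scheduled alike in both arms.
- **Other detection is possible.** Section 7.21 leaves clinical assessment in pregnancy to national maternity guidelines, obstetric assessments in Appendix 5 cover both arms, and the delivery chart audit records complications.

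The last point is why a reader should not infer that urine abnormalities can be found in one arm only. What the text supports is that *study-scheduled* urine exists in one arm only. The documents do not say whether routine care includes urine tests or whether their results are abstracted. If it does, it applies to both arms, and Arm A still has one test more.

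A reader might also take the figure in section 1.10, "Grade 1 proteinuria (1+) occurred in 6% of subjects receiving TRUVADA in the iPrEx trial", as a background rate and expect 421 × 6% ≈ 25 v 0 (p = 4 × 10⁻⁸). The documents do not support that. It is an on-drug rate, at a grade below the 10.3 threshold, from a trial that enrolled only males and transgender females. Nor does any section plan to compare Arm A's urine in pregnancy with Arm B's after weaning, so that confounded contrast should not be attributed to the plan.

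None of this removes the unequal schedule or supplies a rule that keeps its results out of the count.

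**Conclusion.** The plan as written builds arm-dependent detection into one component of the adverse-event comparison: one study urine test per woman in Arm A within the primary window, none in Arm B. The conclusion rests on the text of 7.8 and on the absence of urine elsewhere, and needs no assumed rate. Its size is unknown. The urine-only range runs from negligible (2 v 0 at 0.5%) through 4 v 0 at 1% to a nominally significant 8 v 0 at 2%, assuming equal true rates, detection only by study urine and every abnormality recorded as an event. In the all-event comparison the same abnormalities have a smaller effect (p of 0.31 or more at 2% when at least 5% of women have another event). It would not be right to infer that the primary result will be driven by this, or that the named main outcomes are biased. It is a limited defect that should be closed before the SAP is final.

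**What to change.** **Minimum change.** State in 10.4, or in the SAP that 10.4 says is still to be developed, that urine findings from the drug-triggered 7.8 visit are excluded from the randomised adverse-event comparison and reported descriptively by arm. Say in 7.8 what the urine is analysed for, and reconcile 7.8 with Appendix 5. Cost: one SAP sentence and an editorial correction.

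**If urine is to be compared between arms.** Add a urine row to Appendix 5 at enrolment, before any drug, and at the first 4-weekly antenatal visit, in both arms. Compare only these concurrent tests. The 7.8 on-drug check stays as it is, and its post-weaning Arm B results stay outside the randomised comparison. Cost: with 442 women per arm (10.3), two visits in two arms make 442 × 4 = 1,768 tests. Arm A's four-week test already exists under 7.8, so 442 × 3 = 1,326 are extra, all at visits women already attend.

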7.9 Follow-up Visits until Delivery and Post-delivery

Following enrolment, women will follow the schedule of evaluations in Appendix 5. Women will remain on their assigned treatment arm until cessation of breastfeeding and thereafter follow their choice of either continuing or discontinuing ARV PrEP through the 18 month postpartum visit. Each participant will have follow-up visits approximately every four weeks (28 days) until delivery and following 72 hour postdelivery assessment the participant will be given an appointment for 2 weeks, 6, 10, 14 weeks and thereafter 4 weekly visits until week 74 (approximately 18 months post-delivery) at the study clinic.

7.10 Follow-up Visit <72hours Post Delivery

Participants will be advised to inform the staff by sending a text message when they are admitted to the Labour Ward of the adjacent Hospital. Nursing staff from the research site will also conduct daily postnatal ward rounds to track study participants. A postnatal study visit will be conducted within 72 hours. A maternity chart audit and further clinical assessments of mother and child will be completed prior to discharge from the hospital. The maternity chart audit will specifically be done to record any complications since the last study visit through admission and during the labour process. Pregnancy outcomes will be recorded in the maternal case report form. Infant assessment and mother's intention to breastfeed will be documented in the infant's case report form. Women will be dispensed to women in the Treatment Arm. All participants will have a repeat HIV test, and blood drawn for chemistry and haematological investigations and for storage.

7.11 Follow-up Visits Post Delivery

Subsequent post-delivery visits will be scheduled for weeks 2, 6, 10, 14, 18 weeks, and thereafter monthly until 18 months postdelivery. Study product discontinuation could occur at cessation of breastfeeding for participants in the Treatment Arm who choose not to continue PrEP. And study product will be dispensed to participants in the Control Arm who choose to commence PrEP post cessation of breastfeeding. Study product will be distributed until 74 weeks and thereafter participants will be referred for ongoing PrEP at the nearest PrEP Demonstration Site at a public health clinic.

7.12 At Follow-up Visits during Product Use

At follow-up visits antenatal week 4 through week 74, study staff will:

- Update contact information (when necessary);
- Conduct pill count of product returned by participant, and document any product returned to participant;
- Collect information on adherence to the daily pill-taking regimen;
- Conduct risk reduction counseling, including pre- and post-test HIV counseling and distribute condoms;
- Conduct study product adherence counseling;
- Conduct contraceptive counseling as appropriate, re-supply contraceptive method as needed;

- Collect blood by venepuncture (10ml) and:
 - Perform HIV rapid antibody testing according to the algorithm described at the enrollment visit.
 - ✓ Test for ALT, AST, creatinine and phosphorus. If results are abnormal, repeat regularly until resolution to ≤ Grade 1 or until stabilization. Any required followup will be done per local standard of care.
 - ✓ Store plasma and ULPC aliquots for HIV PCR testing, QA and confirmatory laboratory testing as needed. Also store one plasma aliquot (if sufficient sample available) and one serum aliquot for potential future HIV related research;
 - ✓ Screen and treat other STIs using the syndromic management approach
 - Collect cervical/vaginal swabs for storage and subsequent screening for STIs using molecular techniques.
- Conduct adverse event assessment as per the US Division of AIDS Adverse Event Reporting and Toxicity Grading;
- Conduct physical and/or pelvic examination if clinically indicated; and
- Record medications taken since last visit.
- Complete the Final Status CRF if the participant does not require further follow-up due to risk of Hepatitis B flare and/or HIV seroconversion.

Participants will be allowed to complete each follow-up visit up to five days prior to and two (for the week 4 follow-up visit) or four (for later follow-up visits) days after their next 4-week (28 days) target visit date. If participants complete a visit outside the given window for that specific visit, the visit will be regarded an interim visit and an appointment for the next scheduled visit will be given.

7.13 Followup Visits for Infants

Infants will be assessed at birth, 26 weeks, 50 weeks and 74 weeks. In addition to a full physical examination, a blood sample will be drawn for assessing renal function (Creatinine Clearance) and Hormonal growth factors. For infants exposed to TDF/FTC an additional blood sample will be collected for a drug level assessment. At each visit the following growth parameters will be recorded: weight, height and head circumference. Infant feeding modality will be recorded at each visit. Cessation of breastfeeding is defined as 28 days after last exposure to breastmilk.

7.14 Followup Visits for Women who Seroconvert during Study Participation

This section applies to enrolled participants who test HIV antibody positive on or prior to week 74 and participants who are HIV antibody negative and HIV PCR (RNA or DNA) positive at enrollment or any follow-up visit. Prior to initiation of the clinical trial, site-specific seroconverter plans will be made in consultation with the Department of Health to ensure specific provisions for care and treatment according to the standard treatment guidelines. Study clinicians may share relevant laboratory results with the referral centre care providers provided that the participant provides verbal consent; such consent will be documented in the participant's file.

Any participant who is diagnosed as HIV positive at a follow-up visit will have her study product withdrawn at that study visit. She will receive post-test counselling. If testing of a second sample does not confirm the initially positive result, she may continue using study product. If the participant tests positive on the first sample and refuses to provide a sample for confirmatory testing, her product will be interrupted until a confirmatory test is done. Partners may come to the clinic for voluntary counselling and testing (VCT) according to site-specific SOPs. Participant will be asked if she still agrees to stay in the study until the last scheduled study visit (74 weeks). She will be referred to treatment

centres for appropriate care and treatment according to the site-specific seroconverter care plan and to ongoing HIV treatment or acute HIV infection trials where available. Effective referral will be facilitated by the study counsellors, who will provide voluntary one-on-one counselling and assistance to women in accessing health care or social support services (including help with transportation and communication with health care providers concerning health needs). The counsellors and/or other study staff will also follow up to ensure that participants have secured needed care or services and to determine any problems encountered by women referred from the trial.

When a participant tests HIV positive on the first sample according to the study algorithm, she will be counselled and asked to immediately provide a second sample (10ml in EDTA tube) for a repeat of the HIV algorithm tests as confirmation of the first positive result. According to site SOPs the following samples will also be taken either immediately after the first sample is positive or after the second sample has confirmed the first positive result:

• 10ml in EDTA tube for HIV PCR, HIV-1 viral load and resistance testing;

and,

• 2ml in BD CD4 stabilization tube or 3ml in EDTA tube for CD4 count;

A plasma aliquot will be stored (long term storage) if sufficient sample is available for potential future HIV related research (if participant consented). If the visit of the HIV diagnosis does not coincide with a visit in which secondary endpoints are assessed, another 5-10ml blood in serum tubes (dependent on the site, see site specific lab SOPs) will be collected and tested for AST, ALT, phosphorus and creatinine; a serum aliquot will be stored (long term storage) for potential future HIV related research (if participant consented). HepBsAg testing will be done if appropriate. Procedures for early product withdrawal will also be done.

Samples from her previous visit(s) will be tested by HIV PCR to better determine the infection time and length of exposure to Truvada while HIV infected. Samples from visits in which she was HIV PCR positive but HIV antibody negative will also be tested for resistance and drug levels. At her first follow-up visit after the diagnosis (week 4 post diagnosis), HIV testing according to the study algorithm will be repeated. HIV testing will stop if the first algorithm testing gives a positive result. At each monthly visit post HIV diagnosis, study staff will:

- Update contact information (when necessary);
- Update her medical history, including her medication;
- Conduct further risk reduction counselling and distribute free condoms

7.15 Followup Visits for Children Born to Women who Seroconvert During Pregnancy or Breastfeeding

All HIV exposed infants will continue with study followup until 18 months of age.

Infants born to women who seroconvert during pregnancy will have a HIV DNA PCR test performed at birth and 3 monthly thereafter until cessation of breastfeeding. These infants will also receive antiretroviral prophylaxis (according to the National PMTCT Guidelines) commencing at birth until breastfeeding cessation.

Infants being breastfed by a mother who seroconverts during breastfeeding will have a HIV DNA PCR test performed at the visit when the mother's HIV status is confirmed and 3

monthly thereafter until cessation of breastfeeding. The infant will commence antiretroviral prophylaxis according to the National PMTCT Guidelines.

Infants with confirmed HIV infection (Positive HIV DNA PCR on 2 separate specimens) will be managed according to the National Treatment Guidelines and in addition to routine haematological and chemistry tests al blood sample will be drawn for resistance testing.

